### 6.2.2 Neurological Assessment

The patients will undergo a standardized clinical neurological examination. The neurological tests are performed in order to detect possible mild signs of neuromuscular disease such as disturbance of strength, balance, and coordination. The tests and the results may be modified and adapted to age in children younger than 6 years. The overall neurological status will also be assessed, since some children may refuse to perform all parts of the described neurological status and other kind of neurological assessment will be made during the examination of those children.

The neurological examination includes:

- Extremity reflexes
- Romberg (balance and coordination)
- Walk on a line, 2 meters (balance and coordination)
- Jumping on 1 leg 10 times, left and right (balance and coordination)
- Finger-nose (coordination)
- Mimic (cranial nerves)
- Babinski reflex (central function)
- Muscle strength (shake hands) biceps, triceps, distal extensors, and flexors
- Overall neurological status

These examinations may also be repeated between scheduled visits at the discretion of the investigator. If any signs of neurological dysfunction are detected, the patient should be referred to a pediatric neurologist for further evaluation.

Additional studies will be performed to evaluate the effect of GABA or GABA/GAD on relevant biochemical and hormone concentrations as outlined in the Table below and also to monitor for any possible adverse effects.

**Table 3. Schedule of Study Events**

	At Baseline	1mo post baseline (+/- 1 week)	5mo post baseline (+/- 1 week)	8mo post baseline (+/-1 week)	12mo postbaseline (+/- 1week)
Informed Consent	X (or before)				
Randomization	X				
Gad-alum or placebo injection a	X	X			
Oral GABA or placebo administration starts	X				
Medical History	X				

Vital Signs	X	X	X	X	X
Ht	X	X	X	X	X
Weight	X	X	X	X	X
Physical Exam + Neurological	X	X	X	X	X
Hgb A1C	Done as standard of care at every visit.		Obtain results from chart		
Growth Rate	X	X	X	X	X
Hx of DKA	X	X	X	X	X
Autoimmune antibodies	Done as standard of care at diagnosis. Obtain and document results.		X		X
Mixed Meal Tolerance Test ( glucose, glucagon, C peptide, )	X	X (only fasting and 90 min samples)	X (only fasting and 90 min samples)		X
CBC with diff	X		X		X
Hx of Hypoglycemia	X	X	X	X	X
Complete Metabolic Profile	X		X		X
Glucagon( fasting), glucose, C-peptide	X	X	X		X
Urine Pregnancy test (for menstruating females)	X	X	X	X	X
Total Daily Insulin Dose( U/kg)	X	X	X	X	X
Medication Review/ Concomitant Medications	X	X	X	X	X
Cell Activation Markers	X		X		X
Inflammatory Cytokines	X		X		X
Skin exam: injection site: b	X	X	Ask regarding any issues after last injection. X		
Urinalysis (if available) for microalbuminuria and creatinine and C-peptide	X	X	X	X	X
Adverse Events	X	X	X	X	X
Proinsulin	X		X		X

a GAD-alum/Placebo administration: The target date for the second GAD-alum/Placebo administration will be set in accordance with baseline (i.e. the first injection, Visit 1) so that the second dose will be 1 month post first dose.

b Inspection of injection site before and 60 minutes after injection by investigator or nurse

### 6.3 Patient Compensation

Children will receive \$60 at each visit that requires a mixed-meal tolerance test.

#### 6.4 Patient Management

During the study period, all participants will receive intensive management of their diabetes. The goal of treatment will be to keep HbA1c levels within the currently recommended American Diabetes Association age-specific target range in the absence of significant or severe hypoglycemia or diabetic ketoacidosis.

**All insulin dose adjustments, at either the clinic visit or by phone consultation, are at the discretion of the UAB Pediatric Endocrine Division staff (physicians, diabetes nurse practitioners, diabetic nurse educators) as per our usual type 1 protocol.**

#### 6.5 Rescue Therapy:

Hypoglycemia (low blood sugar) is frequently encountered in diabetics, it could potentially occur after starting GABA or GABA/GAD treatment. All diabetic children and/or their parents are routinely trained to treat hypoglycemia by Children's of Alabama diabetes educators. As standard procedure, all patients have glucagon available if a low blood sugar has rendered them unresponsive. The parents and subjects are provided the research teams contact information and there is a doctor on call 24hrs a day.

#### 6.6 Withdrawal of Participant Consent and Discontinuation of Study Drug:

Study participation may be discontinued for any of the following reasons:

- a. Subject decision to withdraw consent for study
- b. Evidence of allergy to administered products
- c. Intolerable adverse event as judged by study investigator and participant

If the PI chooses to remove the participant from study dosing, rationale will be provided to the participant. If the study drug is discontinued, unless the subject withdraws consent, the subject will be followed for the full treatment period and all data will be collected as scheduled. Attempt will be made to schedule an early end of study assessment in the case of study drug discontinuation. If more than one participant have the same SAE that are thought to be related to treatment compound, the PI and Co-Investigators will meet to discuss whether or not a change in protocol is called for. This information will also be assessed by the independent safety monitoring board. This decision would be reported to the IRB.

#### 6.7 Data Collection and Assays:

Subject visits will consist of a baseline visit and subsequent visits as noted above. The data noted in the table above will be collected by study personnel and stored in a locked office and on a password-protected UAB computer. All laboratory specimens will be collected by study personnel, labeled with the study participant's unique identifier and date of collection, and then stored at -80°C in [name] lab. Analysis of all laboratory measurements will be completed at the conclusion of the study.

- 1.) *Hemoglobin A1C*: Measured by latex immunoagglutination inhibition methodology( DCA 2000, Siemens-Bayer)
- 2.) *Mixed Meal Tolerance Test*: After an overnight fast, the patients will have an IV placed and will drink Boost. They will have C-peptide and glucose and glucagon levels drawn at 10 minutes prior to dose (-10), 0, 15, 30, 60, 90, and 120 min. The C-peptide, glucagon, and glucose levels will be assayed by the UAB Metabolism Core of the Clinical Nutrition Research Center (CNRC). At the 1 and 5 month visits, only a fasting and 90 minute sample are obtained. A recent 2013 article confirms that this 90- minute sample alone correlates significantly with the integral of the C- peptide as a function of time curve, oft-called the AUC [21].
- 3.) *Pancreatic Antibodies*: GAD-65, ICA512 and Anti-Zinc Transporter 8 samples are collected as standard of care at initial diagnosis. We will use these results as our baseline. Follow-up samples will be collected at the visits noted in the Table. Samples will be assayed at ESOTERIX Laboratory Services, Inc..
- 4.) *CBC with manual differentiation*: Performed at baseline and at the visits noted in the Table, and assayed in the hematology lab of Children's Hospital Alabama

- 5.) *Complete Metabolic Profile*: CMP will be monitored at the visits noted in the Table, and assayed in the chemistry lab of Children's Hospital Alabama.
- 6.) *Glucagon*: Glucagon levels will be measured under fasting conditions at the visits noted in the Table, and during the Mixed Meal Tolerance Tests. Assays will be conducted by UAB Metabolism Core of the Clinical Nutrition Research Center (CNRC).
- 7.) *Height*: Collected at each visit
- 8.) *Weight*: Collected at each visit to make dosing adjustments in the GABA .
- 9.) *Medications*: We will review total daily insulin dose and compliance. We will review all other non-study medications which the patients are taking.
- 10.) *Date of Birth*: Obtained at baseline screening.
- 11.) *Medical History*: Will be obtained at screening and updated as needed throughout the study.
- 12.) *Demographics*: Collected at baseline.
- 13.) *Adverse events/Serious adverse events*: Assessed for adverse events and serious adverse events following the baseline visit.
- 14.) *Cell Activation and Inflammation Markers*: Since GABA has been shown to possibly improve inflammation and cellular activity in animal studies we will evaluate for inflammatory and cell markers at varied points in the study. We propose a detailed immune analysis strategy that has 3 arms: (1) analysis of functional CD4 and CD8 subsets (effector vs regulatory) We will perform immunophenotyping studies of the peripheral CD4 and CD8 subsets at baseline and at the 5 and 12 month study visits with monoclonal antibodies specific for CD3, CD4, CD8, CCR4, CCR5, CCR7, CXCR3, CXCR5, CD25, CD28, CD38, CD39, CD45RA, CD45RO, CD62L, CD127, Helios, Foxp3, and PD-1 [BD Biosciences, R&D Systems, eBiosciences] Intracellular cytokine staining of PMA/Ionomycin-anti-CD3/CD28, GAD65 peptivator (Miltenyi Biotec), and tetanus toxoid-stimulated cells will also be examined with monoclonal antibodies to IFN- $\gamma$ , TNF- $\alpha$ , IL-13, IL-10, and IL-17A (BD Biosciences, eBioscience) We expect to observe a decrease in CD4 and CD8 T cell effector cell populations secreting IFN- $\gamma$  and a concomitant increase in CD4 Treg cells (CD4+/CD25+/FoxP3+) that secrete IL-10. Human multi-color flow cytometric analysis will be performed as previously described. (2) functional assays of T cell responses after GABA exposure. we will perform T cell proliferation (CFSE dilution or cell counting kit-8 assays and primary recall assays as previously described to determine if GABA treatment has an effect on decreasing effector cytokine production of CD4 and CD8 T cells and a concomitant increase in Treg cells as described above. Briefly, PBMCs will be purified from fresh blood and stimulated with PMA/Ionomycin. Dynal beads conjugated with anti-CD3 and anti-CD28, GAD65 Peptivator peptides and tetanus toxoid. Supernatants will be collected and the levels of cytokines and chemokines produced by activated T cells will be determined with a Milliplex Human Cytokine/Chemokine Magnetic Bead panel (3) monitoring of serum autoantibody expression {both number of autoantibodies expressed, as well as changes in titer} over the course of the study. The presence and number of positive autoantibodies correlates not only with diabetes diagnosis, but also with degree of beta cell destruction and progression of disease. We are planning subgroup analyses to see if GABA and or GABA/GAD combination have different efficacies based on antibody titers and number of positive antibodies (i.e. participants who are likely to be slow- or fast- progressors). We also want to determine if the number of positive autoantibodies per participant changes, either increases, or decreases, with GBA therapy. Obviously we understand that autoantibodies are not directly pathologic to beta cells, but they may serve as an epiphenomena/surrogate marker for the degree of beta cell destruction. We also propose to add the pro-insulin/C-peptide ratio as a marker of beta cell health. We have arranged with our Metabolism Core Lab at UAB to run the proinsulin levels. For participants who have already completed some study visits, these assessments can still be run from the samples previously collected. HLA (Human Leukocyte Antigens will be performed per [name]. This will be done on samples already collected for the Cell Activation and Inflammatory Markers. The genes in HLA are reported to account for 40-50% of the familial aggregation of Type 1 diabetes. There are certain genes within the HLA typing that have been shown to cause a rapid decrease in  $\beta$ -cell function, whereas other genes seem to have a more gradual destruction. We feel this information can be most beneficial in our research concerning how Type 1 progresses and does the HLA typing effect how these patients respond to the GABA/GAD therapy. Diamyd agreed to fund the additional cost of the research.
- 15.) *Urine pregnancy test*: at each visit for menstruating females.
- 16.) *Skin inspection*: and reports of problems with injection site at baseline and the 1 month visit, as well as the 5 month visit to capture any reports of problems after the second injection.
- 18.) *Physical examination including neurological assessment and vital signs*.
- 19.) *Assessment of number of hypoglycemic events and DKA's*.
- 20.) *Urinalysis for microalbuminuria, creatinine, and C-peptide (if available)*

## 7.0 Adverse Event Reporting and Safety Monitoring

### 7.1 Adverse Events:

An adverse event (AE) is any untoward medical occurrence in a patient or clinical investigation subject administered a pharmaceutical product, and which does not necessarily have to have a causal relationship with this treatment. An AE can therefore be any unfavorable and unintended sign (including an abnormal laboratory finding, for example), symptom, or disease temporally associated with the use of a medicinal product, whether or not considered related to the medicinal product.

All treatment emergent AEs will be recorded from the baseline visit forward (First dose of study drug) for the duration of the study on source documents (i.e., original documents, data, and records). AEs include those reported spontaneously by the subject and those noted incidentally or as observed by the investigator or study personnel. To avoid vague, ambiguous, or colloquial expressions, the AE will be recorded using standard medical terminology that is as specific as possible, rather than the subject's own words. Whenever the investigator is confident in making a unifying diagnosis, all related signs, symptoms, and abnormal test results should be grouped together and recorded as a single AE (e.g., cough and rhinitis should be reported as an "upper respiratory tract infection").

All clinically significant abnormalities noted upon physical examination, or other diagnostic test results should be reported as an AE, except for baseline measurements that may be considered part of the medical history. In addition, all clinically significant AEs that continue at Study Termination should be followed up by the investigator and evaluated with additional tests if necessary, until the underlying cause is diagnosed or resolved, or is determined to have resolved without sequelae. All AEs will be evaluated for intensity and causal relationship with use of the study medication (or study procedures if applicable) by the investigator.

AEs that occur following completion of study termination/early termination procedures will be recorded on the AE page of the source documents only if the investigator considers the event as clinically significant and as related to study medication or study procedures. All adverse events that are deemed to be serious and meet the definitions provided in section 7.2, for serious adverse events will be reported as "SAE's."

## 7.2 SAEs

Any AE that results in any of the following outcomes will be considered an SAE. The following outcomes are defined according to Code of Federal Regulations (CFR) Title 21 part 312.32.

An SAE is an AE, occurring at any dose that fulfils 1 or more of the following:

- Death
- Life-threatening situation (Subject was at risk of death at the time of the event. This does not refer to an event that might have caused death if it was of greater intensity.)
- Inpatient hospitalization or prolongation of existing hospitalization
- Persistent or significant disability or incapacity
- Congenital anomaly or birth defect
- Important medical events that may not result in death, be life-threatening, or require hospitalization but may jeopardize the subject and may require medical or surgical intervention to prevent one of the above outcomes (based upon appropriate medical judgment), e.g., allergic bronchospasm requiring intensive treatment in an emergency room or at home, blood dyscrasias or convulsions that do not result in inpatient hospitalization, or the development of drug dependency or drug abuse.

## 7.3 Methods for Collection and Recording of Adverse Events

All patients are carefully monitored for occurrence of any AE. At each clinic visit/contact after baseline AEs will be collected with a non-leading question such as "Have you had any new or worsening health problems since the previous visit/last contact?" as well as reporting events directly observed or spontaneously volunteered by the patient.

Any abnormal findings in physical examination, vital signs, and clinical laboratory tests must also be reported as AEs.

All reported AEs are to be recorded in the CRF, and an identical entry should be made in the patient's medical record. If no AE has occurred during the study period, this should also be indicated in the CRF/medical records.

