## COHORTS

### 5.3 Inclusion Criteria

- Males and Females 4-18 years of age.
- Be positive for autoantibody GAD-65. If not collected. Collect and send at visit 1.
- They must meet the ADA criteria for diabetes : classic symptoms, plus blood sugar >200mg/dL or fasting blood sugar >126mg/dL
- Enrolled within 4 weeks of diagnosis (+ 1 week window)
- If the participant is female and post-menarchal two forms of contraception must be used during the study if not abstinent. The types of contraception deemed acceptable would be oral contraceptive pills, intrauterine devices and barrier methods.
- Signed informed consent form

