#### 6.2.1 Mixed Meal Tolerance Test

Participants will undergo a mixed meal tolerance test at their outpatient visits as outlined in the instructions below.

- On the evening before the MMTT, subjects will eat a full, standard meal. They will be asked to fast from 9 pm the evening before the test until the MMTT is completed. They should remain hydrated and may consume water during the fast and test.
- Subjects will be instructed to take their long acting insulin the night before the test, but not to administer short-acting insulin for at least 6 hours before the morning MMTT test.

- Participants must have a fasting plasma glucose level in the range of 72-216 mg/dL on the patient's home glucose monitoring device the morning of the test. If for safety reasons, subjects need to eat or take insulin, the visit will need to be rescheduled.
- An Intravenous catheter will be inserted just prior to the test and then GABA or placebo will be given just prior to drinking the Boost High Protein drink (1 cal/mL; 55% carbohydrates, 21% lipids and 24% protein). They will drink 6 ml/kg Boost, up to maximum of 360 ml, to be ingested within 5 minutes. Blood samples from an intravenous catheter are collected 10 minutes prior to the meal (-10), at the time of ingestion (0), and at 15, 30, 60, 90 and 120 minutes thereafter. This schedule will be followed at the baseline and 12 month visits. At 1 month and 5 month visits only a fasting and 90 min sample will be taken. There will not be a MMTT on month 8.
- 3 cc's of urine (if available) will be placed in an aliquot tube and frozen for evaluation of urine C-peptide. The remaining sample will be used for evaluation of microalbuminuria and creatinine levels.

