#### 7.4 Grading and Attribution

##### 7.4.1 Intensity

The study site will grade the intensity of adverse events experienced by study participant according to the criteria set forth in the National Cancer Institute's Common Terminology Criteria for Adverse Events (CTCAE) Version 4.0. This document provides a common language to describe levels of severity, to analyze and interpret data, and to articulate the clinical significance of all adverse events. Adverse events will be graded on a scale from 1 to 5 according to the following standards in the NCI CTCAE manual:

Grade 1 = mild adverse event

Grade 2 = moderate adverse event

Grade 3 = severe and undesirable adverse event

Grade 4 = life threatening or disabling adverse event

Grade 5 = death

All adverse events will be reported and graded whether they are or are not related to disease progression or treatment.

NOTE: A distinction should be drawn between serious and severe AEs. The term "severe" is used to describe the intensity (severity) of a specific event (as in mild, moderate, or severe pain); the event itself, however, may be of relatively minor medical significance (such as severe headache), and does not necessarily need to be considered serious. The term "serious" is used to describe an event based on an event outcome or actions usually associated with events that pose a threat to a patient's life or functioning. Seriousness (not severity) serves as a guide for defining regulatory reporting obligations.

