#### 9.0 Data Analysis:

Baseline demographic and other (e.g., weight) characteristics will be compared between the treatment groups using t- and chi-square tests (or their non-parametric equivalents) for continuous and categorical variables, respectively, in order to demonstrate the success of the randomization process. The primary outcome measure is C-peptide level, which is measured at multiple time points during the study. As is standard practice, the post-stimulus area under the curve (AUC) will be calculated in addition to mean and peak values. The main analysis will focus on a comparison of the baseline and the > 12-month post baseline C-peptide measurements. Analysis of covariance will be used to compare changes in C-peptide levels between the treatment groups. For these analyses the 12-month post baseline measurement will serve as the dependent variable; there will be two independent variables: (1) a binary variable for treatment group and (2) the baseline C-peptide measurement. This is a standard analytical approach for study designs of this type. Given that GABA may affect  $\alpha$ -cell glucagon secretion, possible changes in the circulating concentrations of this hormone will be appraised. In the unexpected event that the treatment groups are not similar with respect to specific demographic and other characteristics, these measurements will also be considered as potential confounders in the aforementioned analysis. A similar analytical approach will be used for the other study outcomes of interest besides glucagon, i.e., hemoglobin A1C, insulin dose/kg body weight/24 hours. Mixed statistical models will be used to conduct longitudinal analyses of C-peptide and hemoglobin A1C measurements, and daily insulin requirements, incorporating all three measurements. All analyses are conducted on an intention to treat basis.

Adverse events and other safety data will be summarized descriptively.

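### Sections 7.1 and 7.3 give conflicting rules on which abnormal findings are adverse events; read literally, 7.3 puts diabetes itself into the AE totals.

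*Combined protocol and SAP*

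**What the plan says.** Two current sections of the protocol cover the same findings.

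- Section 7.1: "All clinically significant abnormalities noted upon physical examination, or other diagnostic test results should be reported as an AE". The section also limits recording to treatment-emergent events from the first dose, excepts baseline measurements that may belong to the medical history, and lets related abnormal results be recorded as one AE when the investigator is confident of a unifying diagnosis.
- Section 7.3: "Any abnormal findings in physical examination, vital signs, and clinical laboratory tests must also be reported as AEs". It repeats none of those limits.

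Section 7.4.1 keeps disease-related events in the record: "All adverse events will be reported and graded whether they are or are not related to disease progression or treatment". The planned analysis in Section 9.0 is one sentence: "Adverse events and other safety data will be summarized descriptively".

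For low glucose, Section 6.2 lists glucose records as well as reports of hypoglycaemia, Table 3 schedules a hypoglycaemia history and a DKA history at all five visits, and Section 6.7, item 19, provides for "Assessment of number of hypoglycemic events and DKA's".

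**The concern.** In most trials, a loose rule on laboratory abnormalities adds only noise to the AE listing. Here the disease under study is itself a laboratory abnormality, present in every child and measured repeatedly. Under 7.3 alone, a routine high HbA1c or chemistry glucose is an AE that must be graded and attributed separately to GABA and to GAD-alum (Section 7.4). Under 7.1 most such results would not be recorded.

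Safety is part of both objectives and is a secondary endpoint, and its analysis is descriptive, so the counts are the result. HbA1c and glucose are also secondary efficacy outcomes. If they feed the AE totals, the share of children with any AE moves towards its ceiling in every arm, and an arm with better glucose records fewer AEs for that reason alone. Either effect could hide a real excess of other events in an overall row.

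**Working it through.** The plan states no figure on this point, so there is none to reproduce. The check compares the texts and then works an illustration.

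**1. The two rules.** Section 7.3 says any abnormal finding and uses a mandatory verb. Section 7.1 says clinically significant findings and uses should. A high glucose that needs only a routine insulin change is an AE under 7.3 and ordinarily not under 7.1. No sentence ranks the two sections.

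**2. Exposed results.** Table 3 has HbA1c at every visit (four after baseline) and a metabolic profile at months 5 and 12 (two after baseline). Section 6.7 sends the profile to the hospital chemistry laboratory. That it includes glucose is an assumption. With 110 children and no dropout:

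- HbA1c: 110 × 4 = 440
- chemistry glucose: 110 × 2 = 220
- total: 660, or 6 per child

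If 25-100% of these were out of range (assumed), 7.3 read literally would give 660 × 0.25 = 165 to 660 AE entries, or 1.5 to 6 per child.

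**3. Children with at least one glucose AE.** Count chemistry glucose only (two results per child). Let p be the chance that a result is abnormal, q = 1 − p, and r the within-child correlation. Then P(none) = q² + r·p·q. Both p and r are assumed.

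**4. Effect on an any-AE comparison.** If a proportion π of an arm has some other AE, independently of glucose, and p is equal across arms, then P(any AE) = 1 − (1 − π) × P(none). A difference between arms in π is therefore multiplied by P(none). The last column applies this to a true difference of 20 points.

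| p | r | P(none) | At least one glucose AE | 20 points shows as |
|---|---|---|---|---|
| 0.40 | 0 | 0.36 | 64% | 7.2 |
| 0.40 | 0.5 | 0.36 + 0.12 = 0.48 | 52% | 9.6 |
| 0.80 | 0 | 0.04 | 96% | 0.8 |
| 0.80 | 0.5 | 0.04 + 0.08 = 0.12 | 88% | 2.4 |

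Example with p = 0.40, r = 0 and other AEs in 40% v 60%: 1 − 0.6 × 0.36 = 78.4% against 1 − 0.4 × 0.36 = 85.6%, a difference of 7.2 points.

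**5. Effect of 7.1's limits.** Counted singly, abnormal chemistry glucose gives 220 × 0.4 = 88 to 220 × 0.8 = 176 AEs. Grouped to one per child, it gives 110 × 0.52 = 57 to 110 × 0.96 = 106. Grouping lowers the number of events but leaves the any-AE proportion in step 4 unchanged, because the child still has one AE. If staff instead regard diabetes as present before the first dose and so not treatment-emergent, the count could fall to zero.

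**6. Direction.** If an active arm had a 10-point lower chance of a high value per visit (assumed), it would lose 2 × 0.10 = 0.20 AE per child when results are counted singly. That is 43 × 0.20 = 8.6 events in the GABA arm or 30 × 0.20 = 6 in the combination arm, with no difference in tolerability.

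**The case against.** The strongest reply is that the protocol should be read as a whole. Section 7.1's treatment-emergent limit, baseline exception and grouping rule are also in force, and diabetes precedes the first dose in every child. Sensible staff would not log each high glucose. This stands in part: it shows that the literal count is an upper reading. It does not settle the matter, because 7.3 uses the mandatory verb, grouping depends on the investigator's confidence, and a child's repeated high values could make zero, one or several AEs.

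Section 9.0 also names no total-AE or any-AE row, and it covers other safety data besides AEs. That is fair. The harm falls on overall summaries if they are made, and the AE table is not the only safety summary.

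Some stronger readings are tempting, but the documents do not support them:

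- **That low glucose reaches the record only by report.** Glucose records are collected, a hypoglycaemia history is taken at every visit, events are counted, and a low laboratory value would itself be an AE under 7.3. The meal-test rule ("Participants must have a fasting plasma glucose level in the range of 72-216 mg/dL") makes low fasting values unlikely on those mornings but does not restrict later samples. What is missing is a stated route from these data to the AE record, and a threshold.
- **That most accepted fasting values are abnormal.** Of the accepted range, (216 − 126)/(216 − 72) = 62.5% lies above the fasting cut-off in Section 5.3. That is a share of interval width, not a rate, and the cut-off is an eligibility criterion.
- **That meal-test glucose counts too.** Those samples go to a research core, and Section 6.7 places analysis of laboratory measurements at the end of the study. They are not plainly clinical laboratory tests, so the illustration leaves them out.

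**Conclusion.** The conflict between 7.1 and 7.3 is real and unresolved. In this population it bears on any overall AE count or any-AE proportion, which would depend on the rule followed and would overlap with secondary efficacy outcomes. Rows by AE term are unaffected, and so are the C-peptide analysis and the sample size.

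The size cannot be fixed from the documents. The ranges of 52-96% of children and 0.8-9.6 points rest on an assumed 40-80% abnormal rate, correlation 0-0.5, glucose being part of the chemistry profile, independence from other AEs, an equal glucose rate across arms, and 7.3 being applied as worded. HbA1c would add to the effect, and treating diabetes as not treatment-emergent could remove it. This is a modest point about the safety summary, worth correcting because the correction is cheap.

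**What to change.** Before database lock and while staff and analysts are still blinded:

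1. Restrict Section 7.3 to clinically significant findings, so that it matches 7.1.
2. Add one sentence: glucose, HbA1c and C-peptide values are analysed as outcomes and are not AEs unless they meet an SAE criterion or need treatment beyond usual insulin adjustment.
3. Add to Section 9.0 that post-baseline hypoglycaemia and DKA counts, which are already collected, are tabulated by arm on their own line. The protocol gives no glucose threshold for hypoglycaemia. The meal-test limit of 72 mg/dL is a scheduling rule, so any threshold is for the study team to choose.

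The cost is a few sentences, with no new visits or samples. The drawback is a blinded reclassification of AEs already entered under 7.3.
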